Appendix 2. Schedule of Events (Recipient) Post-Transplant

		DAYS			WEEKS												
		5	14	28	56	84	16	20	24	28	32	36	40	44	48	52	FOR CAUSE
	VISIT NUMBERS	2	3	4	5	6	7	8	9	10	11	12	13	14	15	16	2, 3
	VISIT WINDOWS (+/- DAYS)		2	3	3	3	3	3	3	5	5	5	5	5	5	5	_, -
	RAL ASSESSMENTS																
Physical Exam	BP, Pulse, Temperature, Respiration, Weight	Х	Х	Х	Х	Х	Х	Х	Х	Х	Х	Х	Х	Х	Х	Х	
Immunosuppressive Meds	Drug Name and Dose	\rightarrow	\rightarrow	\rightarrow	\rightarrow	\rightarrow	\rightarrow	\rightarrow									
Concomitant Medications	Drug Name (Anti-HTN, Prophylaxis, Anti-Viral)	Х	Х	Х	Х	Х	Х	Х	Х	Х	Х	Х	Х	Х	Х	Х	Х
Assessments of Events	AE/SAE, Infections, Rejections, Hospital, Graft Loss, Malignancies, New Onset Diabetes, Death	\rightarrow	\rightarrow	\rightarrow	\rightarrow	\rightarrow	\rightarrow	\rightarrow									
Neurological Assess. for PML	Hx, mini mental, cranial nerve, motor, cerebellar			Х		Х				Х		Х				Х	
	LOCAL LABO	RAT	ORY	ASS	SESSI	MEN	TS										
Hematology Panel	CBC, differential, Platelet			Х		Х				Х		Х				Х	Х
Chemistry Panel / GFR (CKD-EPI and MDRD)- Renal Function	Serum Creatinine, BUN, glucose, sodium, AST, ALT, ALP, bilirubin, albumin, calcium, phosphate			X		Х				X		Х				X	Х
Chemistry- Pancreatic Function	Serum Amylase, Serum Lipase			X		X				X		X				X	Х
Fasting Lipid Panel	Total, HDL, LDL, Triglycerides									Х						Х	
C-Peptide	C-Peptide															Х	Х
Hemoglobin A1c	HbA1c			Х		Х				Х		Х				Х	
Urinalysis	Protein, Glucose, Hematuria, WBC			Х		Х				Х		Х				Х	Х
Trough Levels	Tacrolimus trough levels	Х	Х	Х	Х	Х	Х	Х	Х	Х	Х	Х	Х	Х	Х	Х	Х
Viral Monitoring	BKV and CMV by PCR in blood			Х		Х				Х						Х	
Histology- Renal	Local Read- Banff 2007 Renal																Х
Histology – Pancreas	Local Read- Banff 2011 Pancreas																Х
	NULOJIX® (BELA	ГАС	EPT)	INF	USIO	N D	OSIN	IG			. 			1			
Belatacept Infusion Investigational Arm 	IV, 10mg/kg	X4	X	X	X	X											
Belatacept Infusion Investigational Arm 	IV, 5mg/kg						Х	Х	Х	Х	Х	X	Х	Х	Х	Х	
TACROLIMUS DOSING SCHEDULE																	
Tacrolimus Dosing Control Arm 	Dose adjusted to target trough levels of 8- 12ng/mL to week 24, then 5-8ng/mL thereafter.	\rightarrow	\rightarrow	\rightarrow	\rightarrow	\rightarrow	\rightarrow	\rightarrow									
Tacrolimus Dosing ^{6,7,8} Investigational Arm 	Dose adjusted to target trough levels 5-8 ng/mL to week 24, then 3-5 ng/mL until week 40.	\rightarrow	\rightarrow	\rightarrow	stop												
MYCOPHENOLATE MOFETIL DOSING SCHEDULE																	
Mycophenolate Mofetil	1gm BID, Adjusted based on clinical complications	\rightarrow	\rightarrow	\rightarrow	\rightarrow	\rightarrow	\rightarrow	\rightarrow									

Optimization of Belatacept Usage as a Means of Minimizing CNI Exposure in Simultaneous Kidney and Pancreas Transplantation Version 6.0/ May 14, 2015

Page 98 of 104

		DAYS			WEEKS												
		5	14	28	56	84	16	20	24	28	32	36	40	44	48	52	FOR
	VISIT NUMBERS	2	3	4	5	6	7	8	9	10	11	12	13	14	15	16	CAUSE [,]
	VISIT WINDOWS (+/- DAYS)		2	3	3	3	3	3	3	5	5	5	5	5	5	5	3
CELLULAR CORE LABORATORY- EMORY UNIVERSITY (PI: [name]																	
Intracellular Cytokine Staining	32 mL Blood CPT Tube									Х		X				Х	Х
Flow Cytometry	20-40 mL Blood Cyto-Chex Tube			Х		Х				Х		Х				Х	Х
MA	RKERS OF AUTOIMMUNITY COR	E LAI	BOR	ATO	RY- L	JCSF	F (PI:	[name], M	D)					
Markers of Autoimmunity- PBMC	30 mL Blood Green-Top Vacutainer			Х		Х				Х		Х				Х	Х
Markers of Autoimmunity- Serum	5mL Blood- Red-Top Vacutainer			Х		Х				Х		Х				Х	Х
MOLECULAR CORE LABORATORY- UNIVERSITY OF ALABAMA (PI: [name])																	
Gene Expression, mRNA Profiling (Blood)	2.5 mL Blood- PAXgene RNA Tube			Х		Х				Х		Х				Х	Х
Gene Expression- mRNA Profiling (Urine)	50-100 mL Urine (Pellet)			Х		Х				Х		Х				Х	Х
Gene Expression- mRNA Profiling (Tissue)	1 renal core in RNALater																Х
ASSAYS OF AL	ASSAYS OF ALLOGRAFT INJURY LABORATORY- UNIVERSITY OF ALABAMA (PI: [name])																
Cytokines and Growth Factors	7 mL Blood - Red-Top Vacutainer			Х		Х				Х		Х				Х	Х
Serum Proteins- CTGF, TGFbeta	4.5mL Blood- Light Blue CTAD			Х		Х				Х		Х				Х	Х
Urine Proteins- CTGF, TGFbeta	50-100 mL Urine (Supernatant)			Х		Х				Х		Х				Х	Х
ANTIBO	DY CORE- EMORY UNIVERSITY S	CHC	OOL	OF M	IEDI	CINE	E (PI:	[name]	, PHI	D)				
Non-HLA Ab/Anti-HLA Antibodies / DSA ¹	5 mL Blood - Red-Top Vacutainer			Х		Х				Х		Х				Х	Х
	PATHOLOGY CORE LABORAT	ORY-	- UCS	SF (P	I: [name], I	MD)	•			•	•		
Histology/Immunohistochemistry - Renal	5 slides (1-Trichrome or unstained, 1- PAS, 3-H&E) AND FFPE tissue (remaining block) AND C4d and SV40																Х
Histology- Pancreas	slides (if available) 4 slides (1-Trichrome/ unstain, 3-H&E)																Х
VIRAL MONITORING CORE- EMORY UNIVERSITY (PI: [name])																	
Viral Monitoring by PCR (EBV) AND Viral	4 mL Blood in EDTA Lavender-top			X	111	X		5 n w		X		X				X	Х
Monitoring Assay Development: BLOOD	Vacutainer Tube			Л		Л				Л		~				л	Λ
Viral Monitoring by PCR (CMV, BKV, JCV, HHV6, HHV7) AND Viral Monitoring Assay Development (HHV3 (varicella zoster), HHV6 (roseola), HHV7 (cofactor CMV), polyoma JC, WC,KI): PLASMA	5mL PPT Tube OR plasma collected from the CPT tubes for Intracellular Cytokine Staining Viral Phenotyping			X		Х				X		Х				Х	Х

1. If a subject develops anti-donor alloantibodies or de novo anti-HLA (PRA >25%), the test must be repeated on a fresh sample and confirmed within 4 weeks.

2. For Cause Biopsy specimens should be collected at times of graft dysfunction, and prior to initiating therapy.

3. If blood samples are collected for a For-Cause biopsy AND are within 2 weeks of a scheduled visit, then the samples will also be used for the scheduled visit.

4. The first dose of NULOJIX® (belatacept) will be administered approximately 24-48 hours after the last dose of Thymoglobulin® (Anti-Thymocyte Globulin- Rabbit).

5. The results of the non-HLA Ab/Anti-HLA Antibodies/DSA drawn at week 36 will be sent back to the clinical sites in order to make a decision regarding tacrolimus withdrawal at week 40.

6. At week 40, subjects eligible for withdrawal will be weaned over a 4-8 week period based on the protocol.

7. Tacrolimus dosing will be collected following week 44 on subjects who were not eligible for withdrawal or failed withdrawal.

8. During tacrolimus weaning and for 6 weeks post tacrolimus withdrawal, subjects will have weekly labs that include serum creatinine, fasting glucose, amylase and lipase.

Appendix 3. Schedule of Events (Recipient) Post-Transplant (Year 2)

			_,	WE	EKS			FOR CAUSE 2, 3
		56	60	64	68	72	76	
	VISIT NUMBERS	17	18	19	20	21	22	
	VISIT WINDOWS (+/- DAYS)	5	5	5	5	5	5	
	GENERAL ASSESSMENTS							
Physical Exam	BP, Pulse, Temperature, Respiration, Weight	Х	Х	Х	Х	Х	Х	
Immunosuppressive Meds	Drug Name and Dose	\rightarrow						
Concomitant Medications	Drug Name (Anti-HTN, Prophylaxis, Anti-Viral)	Х	Х	Х	Х	Х	Х	Х
Assessments of Events	AE/SAE, Infections, Rejections, Hospital, Graft Loss, Malignancies, New Onset Diabetes, Death	\rightarrow						
Neurological Assess. for PML	Hx, mini mental, cranial nerve, motor, cerebellar			Х			Х	
	LOCAL LABORATORY ASSESSMENTS							
Hematology Panel	CBC, differential, Platelet			Х			Х	Х
Chemistry Panel / GFR (CKD-EPI and MDRD)- Renal Function	Serum Creatinine, BUN, glucose, sodium, AST, ALT, ALP, bilirubin, albumin, calcium, phosphate			Х			Х	Х
Chemistry- Pancreatic Function	Serum Amylase, Serum Lipase			Х			Х	Х
Fasting Lipid Panel	Total, HDL, LDL, Triglycerides			Х			Х	
C-Peptide	C-Peptide						Х	Х
Hemoglobin A1c	HbA1c			Х			Х	
Urinalysis	Protein, Glucose, Hematuria, WBC			Х			Х	Х
Trough Levels	Tacrolimus trough levels	Х	Х	Х	Х	Х	Х	Х
Viral Monitoring	BKV and CMV by PCR in blood						Х	
Histology- Renal	Local Read- Banff 2007 Renal							Х
Histology – Pancreas	Local Read- Banff 2011 Pancreas							Х
	NULOJIX® (BELATACEPT) INFUSION DOS	ING					•	
Belatacept Infusion Investigational Arm 	IV, 5mg/kg	X	X	X	X	X	X	
TACROLIMUS DOSING SCHEDULE								
Tacrolimus Dosing Control Arm 	Dose adjusted to target trough levels of 5-8ng/mL.	\rightarrow						
Tacrolimus Dosing ¹ • Investigational Arm	Withdrawn by week 48 or dose adjusted based on Investigator discretion.							
MYCOPHENOLATE MOFETIL DOSING SCHEDULE								
Mycophenolate Mofetil	1gm BID, Adjusted based on clinical complications	\rightarrow						

1. Tacrolimus dosing is only collected on subjects who were not eligible for withdrawal or failed withdrawal.

2. For Cause Biopsy specimens should be collected at times of graft dysfunction, and prior to initiating therapy.

3. If blood samples are collected for a For-Cause biopsy AND are within 2 weeks of a scheduled visit, then the samples will also be used for the scheduled visit.

Appendix 4. Reduced Follow-Up Schedule of Events (Recipient)

		D	AYS		S	
		28	84	24	36	52
	VISIT NUMBERS	4	6	9	12	16
	VISIT WINDOWS (+/- DAYS)	3	3	3	5	5
ASSESSMENTS	DETAILS					
	GENERAL ASSESSMENTS					
Physical Exam	Blood Pressure, Pulse, Temperature, Respiration, Weight	X	X	X	X	X
Immunosuppressive Medications	Drug Name, Dose, Start and End Date	\rightarrow	\rightarrow	\rightarrow	\rightarrow	\rightarrow
Assessments of Events	AE/SAE, Infections, Rejections, Hospitalizations, Graft Loss, Malignancies, New Onset Diabetes, Death	\rightarrow	\rightarrow	\rightarrow	\rightarrow	\rightarrow
Neurological Assessments for PML	History, mini mental, cranial nerve, motor, cerebellar exam	X	X	X	Х	Х
	LOCAL CLINICAL LAB ASSESSMEN	TS				
Hematology Panel	CBC, differential, Platelet	Х	Х	Х	Х	X
Chemistry Panel	Serum Creatinine	Х	Х	Х	Х	Х
Urinalysis	Protein, Glucose, Hematuria, WBC	Х	Х	Х	Х	Х
Viral Monitoring	BKV and CMV by PCR in blood	Х	Х	Х		
Viral Monitoring	CMV by PCR in blood					Х

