Graft Failure- Renal	90 consecutive days of dialysis dependency.				
Graft Failure-	Return to exogenous insulin therapy or initiation of oral hypoglycemic agents for greater				
Pancreas	than 30 days.				
Insulin	Insulin free.				
Independent					
Premature	A subject will be terminated prematurely from the study if: 1) the subject withdraws consent,				
Termination	2) is lost to follow-up, 3) the investigator or sponsor decision, 4) death, or 5) the subject is				
	found to have a positive TB test.				
Protocol Mandated	Any procedure performed solely for the purpose of this research study, not considered site				
Procedures	specific standard of care.				
Randomized	A subject who met all eligibility criteria; met with the study investigator or designee to				
	discuss the study purpose, requirements (i.e., time requirements, schedule of events, etc.),				
	discussed all risks and benefits, signed the informed consent document and was randomly				
	assigned to one of the two treatment groups.				
Reduced Follow Up	Randomized subjects who are no longer following the assigned study therapy regimen, and				
r i	do not meet the criteria for early termination, will continue to participate in the study for				
1	safety and applicable enupoint assessments.				
Renal Dysfunction	safety and applicable endpoint assessments. Two consecutive readings with an increase in serum creatinine of 25% from baseline.				

Clinical Trials in Organ Transplantation (CTOT) CONFIDENTIAL Protocol CTOT-15

Sensitizing Event	Defined as a blood transfusion, pregnancy, or an event in the opinion of the Investigator		
	would necessitate repeating the PRA.		
Treated Diabetes	Receipt of any oral medication or insulin for the treatment of diabetes for >14 days		
Tuberculosis	TB is defined as a positive TB Skin Test (TST/PPD) or a TB-specific interferon gamma release assay, such as a QuantiFERON®-TB, QuantiFERON®-TB in tube, or a T-Spot®.		
Withdrawn from Study Therapy	Subjects who prematurely discontinue study treatment will be treated according to the site specific standard of care and followed for safety until 52 weeks post-transplant.		
Primary Nonfunction (PNF)	Graft failure that occurs between 3 and 7 days post-transplant.		

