1.5.3 Measures of Cardiovascular and Metabolic Parameters

The following will be measured at baseline, days 28, 84, and weeks 28, 36, and 52, unless otherwise stated below.

- 1. HbA1c.
- 2. Fasting Blood Sugar (FBS).
- 3. Standardized blood pressure measurement and use of anti-hypertensive medications.
- 4. Fasting lipid profile (Total Cholesterol, non-HDL Cholesterol, LDL, HDL, and triglyceride) and the use of lipid lowering medications at baseline, and weeks 28 and 52.

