Five deaths (4 in the CsA group and 1 in the belatacept MI group) occurred and were analyzed according to the intent-to-treat (ITT) principle. Two of these deaths – both in the CsA group – occurred on therapy or within 56 days of the last dose of study therapy. Accordingly, these deaths also are counted under the prespecified safety conventions.

Three other deaths qualify under the ITT principle, but not under the safety conventions because they either never received study drug or the death was an event subsequent to the discontinuation of study drug + 56 days. One death in the CsA group and 1 in the belatacept MI group, occurred > 56 days after the last dose of study therapy. One death in the CsA group occurred in a participant who was randomized, but never treated.

Adverse Events

Overall Adverse Events

The overall incidence of AEs is summarized in Table 1A.

Table 1A:Overall Incidence of Adverse Events Through Day 56 After
Double-blind Period (Randomized, Transplanted and Treated
Population) - Study IM103-100

	No. (%) of Participants		
	Belatacept MI (N=74)	Belatacept LI (N=71)	CsA (N=71)
Adverse Events	73 (98.6)	69 (97.2)	68 (95.8)
Discontinued Due to Adverse Events	13 (17.6)	15 (21.1)	14 (19.7)
Related Adverse Events	43 (58.1)	40 (56.3)	50 (70.4)
Serious Adverse Events	50 (67.6)	52 (73.2)	41 (57.7)
Related Serious Adverse Events	20 (27.0)	23 (32.4)	21 (29.6)
Deaths ^a	0	0	2 (2.8)

• a Includes all deaths up to 56 days after last dose of study therapy, by therapy received. CsA = cyclosporine, LI = less intensive, and MI = more intensive.

The rate of AEs, including AEs resulting in discontinuation, was similar across the 3 treatment groups. The rate of SAEs was somewhat higher for both belatacept treatment groups than for the CsA treatment group. As described below, this difference is due to an increased number of reports of AEs of transplant rejection, not subsequently confirmed as transplant rejection, in the belatacept treatment groups.

The incidence of AEs, by Medical Dictionary for Drug Regulatory Activities (MedDRA) system organ class (SOC) and preferred term, is summarized in Table 1B.

Table 1B:Most Frequent Adverse Events (At Least 10% in Any Group)Through Day 56 After Double-blind Period (Randomized,
Transplanted and Treated Population) - Study IM103-100

	No. (%) of Participants		
MedDRA System Organ Class Preferred Term	Belatacept MI (N=74)	Belatacept LI (N=71)	CsA (N=71)

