8.7 Modification or Discontinuation of Study Therapy

Study treatment may be prematurely discontinued at the discretion of the Investigator for any of the following reasons:

- 1. The subject is unwilling or unable to comply with the protocol.
- 2. The subject experiences graft failure.
- 3. Any clinical AE, laboratory abnormality or intercurrent illness, which in the opinion of the site PI indicates that continued treatment with study therapy is not in the best interest.
- 4. Pregnancy.
- 5. Two consecutive missed NULOJIX® (Belatacept) infusions.

Subjects who prematurely discontinue study treatment will be treated according to the site standard of care and followed until 52 weeks post-transplant. Please refer to Reduced Follow-Up Schedule (Appendix 4). If subjects discontinue study therapy beyond week 52, they will complete the visits outlined in Appendix 3 [Schedule of Events (Recipient) Post-Transplant (Year 2)]. If the subject is unable to return to the study center, the data associated with these visits may be obtained from the subject's local physician.

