	Biopsy-confirmed Incidence of an increase of ≥ 1 CAN/IFTA grade, relative to baseline, at each follow-up assessment	Dichotomous (Banff score <1 vs. ≥ 1)	Proportion + 95% CI	Log-binomial or Poisson regression
	Prevalence of CAN/IFTA grades I, II, III at week 52	Dichotomous (1 outcome for each grade)	Proportion + 95% CI	Log-binomial or Poisson regression (1 model per grade)
Incidence and Severity of Rejection and Anti-donor reactivity	Incidence of Acute Rejection (AR) of renal or pancreatic transplant within the first 52 weeks	dichotomous	Proportion + 95% CI	Log-binomial or Poisson regression
	Banff score of the 1 st observed of renal or pancreatic AR within 52 weeks post- transplant	Ordered categories (3 levels)	Proportion + 95% CI	Proportional Odds model
	Highest Banff score observed within 52 weeks post-transplant for either renal or pancreatic transplant	Ordered categories (3 levels)	Proportion + 95% CI	Proportional Odds model

Page 85 of 104

Response type	Response	Measurement Scale	Summary Statistics	Models to test for treatment effects
	Steroid vs. nonsteroidal treatment for renal or pancreatic AR	dichotomous	Proportion + 95% CI	Log-binomial or Poisson regression
	Prevalence of anti- donor HLA antibodies at week 52 for renal or pancreatic transplant subjects	dichotomous	Proportion + 95% CI	Log-binomial or Poisson regression
Cardiovascular + Metabolic	Fasting blood sugar	continuous	Mean and/or geometric mean + 95% CI	Separate ANOVA or ANCOVA at weeks 28 and 52
	HbA1c (baseline through week 52)	continuous	Mean and/or geometric mean + 95% CI	Mixed effects Repeated Measures ANCOVA
	Blood pressure at weeks 28 and 52	Continuous	Mean and/or geometric mean + 95% CI at weeks 28 and 52	ANCOVA at weeks 28 and 52, with use of blood-pressure drugs as a covariate
	Use of BP medications	dichotomous	Proportion + 95% CI	Log-binomial or Poisson regression
	Fasting lipid profiles at weeks 28 and 52	Continuous	Mean and/or geometric mean + 95% CI	Separate ANOVA or ANCOVA at weeks 28 and 52
	Total daily pill count	continuous	Mean + 95% CI tabulated and plotted over time, by trt. group	Separate ANOVA or ANCOVA at day 85 and weeks 28 and 52 (or Poisson Reg)
Safety (for both renal and pancreatic transplant subjects)	Incidence of death or graft loss or undetectable C-peptide separately and as a composite	dichotomous	Proportion + 95% CI	Log-binomial or Poisson regression
	Incidence of any AE	dichotomous	Proportion + 95% CI	Log-binomial or Poisson regression

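### The reduced follow-up schedule omits HbA1c, fasting glucose, lipids, concomitant drugs and c-peptide, so subjects who stop therapy before week 52 have no scheduled week-52 metabolic measurements

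*Combined protocol and SAP*

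**What the plan says.** Improved cardiovascular and metabolic risk profiles are part of the secondary objective (section 1.3). Section 1.5.3 lists HbA1c, fasting blood sugar, blood pressure with antihypertensive use, and fasting lipids with lipid-lowering use. On timing it says: "The following will be measured at baseline, days 28, 84, and weeks 28, 36, and 52, unless otherwise stated below". Lipids are limited to baseline and weeks 28 and 52. Section 1.5.2 adds week-52 pancreatic endpoints, two of which are defined by c-peptide.

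Table 9 gives the models. Fasting blood sugar and lipids each get "Separate ANOVA or ANCOVA at weeks 28 and 52". Blood pressure gets an ANCOVA at the same two visits with blood-pressure drugs as a covariate. HbA1c gets a repeated-measures model from baseline through week 52.

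For subjects who stop study treatment early, section 8.7 says they are followed to week 52 and adds: "Please refer to Reduced Follow-Up Schedule (Appendix 4". The Study Definitions describe reduced follow-up as applying to randomised subjects who are off assigned therapy and who "do not meet the criteria for early termination, will continue to participate in the study for" safety and applicable endpoint assessments.

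The appendix headed "Appendix 4. Reduced Follow-Up Schedule of Events (Recipient" schedules visits at days 28 and 84 and weeks 24, 36 and 52. Its rows are physical exam (including blood pressure), immunosuppressive drugs, events, neurological exam, hematology, serum creatinine, urinalysis and viral PCR.

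**The concern.** Section 8.7 lists graft failure, adverse events and two consecutive missed belatacept infusions among the reasons for stopping. The Study Definitions count a pancreas graft as failed when the subject has been back on insulin, or on oral hypoglycemic agents, for more than 30 days. A subject withdrawn for that reason stops having scheduled HbA1c and blood glucose just when those values matter most to the metabolic comparison. The missingness can therefore be tied to the outcome. The missed-infusion reason can arise in one arm only, so losses need not be balanced.

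If such subjects are left out, the week-52 comparison of glucose and lipids is no longer between the groups as randomised. It becomes a comparison among subjects who stayed on therapy. The missing-data sensitivity analyses in section 13.2.1 concern eGFR and do not cover these endpoints.

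**Working it through.** **Step 1. Compare the schedules with the endpoints.**

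| Item needed | Appendix 2 (full) | Appendix 4 (reduced) | Effect after discontinuation |
|---|---|---|---|
| HbA1c | Days 28, 84; weeks 28, 36, 52 | No row | Later values missing; earlier visits still enter the repeated-measures model |
| Fasting blood glucose | Glucose in chemistry panel, same visits | No row; chemistry is creatinine only, and the only glucose is in the urinalysis | Lost from the week-28 and week-52 models |
| Fasting lipids | Weeks 28, 52 | No row | Lost from both models |
| Blood pressure | Every visit | Days 28, 84; weeks 24, 36, 52 | Present at week 52, absent at week 28 |
| Concomitant drugs | Every visit | No row | Covariate and drug-use endpoints unscheduled |
| C-peptide | Week 52 and for cause | No row | Week-52 partial-function and pancreatic-loss endpoints (1.5.2) and the undetectable c-peptide outcome (1.5.5) unscheduled |

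The drug row in Appendix 2 reads "Drug Name (Anti-HTN, Prophylaxis, Anti-Viral". It does not name the lipid-lowering drugs that 1.5.3 needs or the glucose-lowering drugs that 1.5.2 needs.

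**Step 2. Who is affected.** Three groups do not move to Appendix 4:
- Subjects with rejection during or after tacrolimus withdrawal stay on Appendix 2, then Appendix 3 (section 8.5).
- For late stoppers section 8.7 says: "If subjects discontinue study therapy beyond week 52, they will complete the visits outlined in Appendix 3".
- Experimental-arm subjects moved to physician-directed therapy by the amendment keep the schedule they are on. Those on Appendix 2 or 3 at that point stay there.

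**Step 3. Is there a rate?** Section 13.3 fixes 30 subjects per arm and gives no discontinuation allowance. The only discontinuation figures in the documents are in Table 1A, for the earlier kidney-only study IM103-100, in the row "Discontinued Due to Adverse Events". They reproduce: 13/74 = 17.6%, 15/71 = 21.1% and 14/71 = 19.7%. Pooled, 42/216 = 19.4% (exact 95% CI 14.4% to 25.4%). That study is not this trial, so the rate d below is an assumption, shown as a range.

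**Step 4. Loss of precision.** With the same fraction d lost in each arm, the number affected is 60d and the number left per arm is 30(1 − d). The standard error of a single-visit difference is multiplied by 1/√(1 − d). The last two columns use a two-sample t-test, two-sided alpha 0.05. They give the difference detectable with 80% power, and the power for 0.736 SD, which is the difference detectable at 30 per arm.

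| Assumed d | Affected of 60 | Left per arm | SE multiplier | Detectable difference | Power for 0.736 SD |
|---|---|---|---|---|---|
| 0 | 0 | 30 | 1.00 | 0.736 SD | 80% |
| 10% | 6 | 27 | 1/√0.90 = 1.05 | 0.777 SD | 76% |
| 20% | 12 | 24 | 1/√0.80 = 1.12 | 0.826 SD | 70% |
| 30% | 18 | 21 | 1/√0.70 = 1.20 | 0.886 SD | 64% |

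These figures apply to week-52 glucose and lipids. They overstate the loss for HbA1c, whose model keeps earlier visits.

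**Step 5. Bias.** Let off-therapy subjects differ from on-therapy subjects by δ within each arm, and let f be the fraction off therapy. Leaving them out of a single-visit model removes f(inv)·δ(inv) − f(ctl)·δ(ctl) from the arm difference. With a common δ this is δ·[f(inv) − f(ctl)], which is zero when the fractions are equal. The documents give neither δ nor f for this trial. In IM103-100 the two belatacept arms differ from control by 17.6 − 19.7 = −2.1 and 21.1 − 19.7 = +1.4 percentage points, so not even the sign of an imbalance can be read from it.

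**The case against.** A reduced schedule is a deliberate choice. The definitions promise only applicable endpoint assessments, and elsewhere say that withdrawn subjects are followed for safety. Appendix 4 keeps serum creatinine, and so eGFR, at week 52. Trimming secondary laboratory tests in a 60-subject phase II trial is defensible. Section 8.3 requires centers to record non-immunosuppressive therapy without limiting this to subjects on therapy, so some drug data may be recovered. Appendix 4 also records graft loss, which by definition captures sustained return to glucose-lowering treatment. All of this stands. It narrows the gap but supplies no HbA1c, blood glucose, lipid or c-peptide value.

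Three stronger readings are tempting, and the documents do not support them.
- A reader might infer from Table 1A that about one subject in five will be affected. Those rates are for adverse-event discontinuation in a kidney-only trial with basiliximab induction, maintenance corticosteroids and a cyclosporine comparator.
- A reader might infer that the cardiovascular and metabolic endpoints cannot be scored at all for these subjects. Blood pressure is taken through week 52, and HbA1c before discontinuation still counts.
- A reader might infer a definite bias in HbA1c from higher discontinuation in the investigational arm. Table 1A shows near-equal rates, the exceptions for tacrolimus withdrawal and for the amendment reduce transfers to Appendix 4 in that arm, and no HbA1c shift is given anywhere.

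**Conclusion.** The gap holds in a limited form. For subjects who stop therapy before week 52 and move to Appendix 4, the plan schedules no later HbA1c, fasting glucose, lipids, c-peptide or concomitant-drug record, although sections 1.5.2 and 1.5.3 and Table 9 call for them, chiefly at week 52. Blood pressure is affected only at week 28 and through its drug covariate.

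The size rests on an assumed discontinuation rate: 6 to 18 of 60 subjects at 10% to 30%. With equal loss in both arms, this raises the standard error of a week-52 glucose or lipid comparison by about 5% to 20%. Bias is plausible because of the reasons for stopping, but neither its direction nor its size can be derived from the documents. The primary endpoint is not the subject of this point. The change is worth making because it is cheap.

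**What to change.** Add to Appendix 4 at week 52: HbA1c, fasting glucose, fasting lipids, c-peptide, and current antihypertensive, lipid-lowering and glucose-lowering drugs. Where Table 9 analyses week 28, schedule the corresponding items, including blood pressure and its drug covariate, at that visit too. Accept values from the clinical record, or from the local physician as section 8.7 already allows when a subject cannot return. State in section 13.2.2 that these endpoints are analysed in all randomised subjects with a value, regardless of therapy status. Name lipid-lowering and glucose-lowering drugs in the Appendix 2 drug row.

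The cost is schedule and eCRF wording, a few routine tests and a drug list. Week 52 already draws blood under Appendix 4; week 28 would need a short visit or a chart lookup. If new draws are no longer feasible, chart retrieval remains possible, and the report should state how many subjects per arm lack each value and why they stopped.
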